4. To compare proportion of patients needing extra prednisone to control flares.
5. To compare the proportion of patients with intra-articular injections.
6. To compare the proportion of patients who have at least one flare confirmed by the investigator during the protocol.
7. To compare the area under the curve of the means of the FLARE at one year with a self-assessment questionnaire.
8. To compare the proportion of patients in DAS28 remission and in DAS28 low disease activity at 7 and 12 months between the groups.
9. To compare the medians of HAQ at 4, 7 months and 1 year between the groups.
10. To compare the medians of RAID at 4, 7 months and 1 year between the groups.
11. To compare the medians of the EQ-5D at 4, 7 months and 1 year between groups.
12. To compare the medians of the FACIT-F at 4, 7 months and 1 year between groups.
13. To compare the proportion of patients with “serious” adverse events at 1 year between the groups.

STAR – Statistical Analysis Plan
V3, June 2023

Page 9 of 96

5) Study Population

a. Inclusion Criteria

- Patients aged ≥ 18 years.
- Fulfilling the 2010 ACR/EULAR criteria for RA.
- Treated with a stable dose of sDMARDs or bDMARDs for at least 3 months.
- Who have been treated with prednisone or prednisolone for at least 6 months.
- With a stable dose of prednisone or prednisolone of 5mg/day for at least 3 months.
- With a DAS28 ≤ 3.2 for at least 3 months.
- Patients with health insurance.
- Patients who have signed a written informed consent form.

b. Non-inclusion Criteria

- Any chronic condition that would need long term corticoid use (e.g. chronic lung diseases).
- Evidence of a flare within the last 3 months.
- Evidence of an allergy or intolerance to hydrocortisone or prednisone.
- Chronic idiopathic, or autoimmune clinical adrenal insufficiency.
- GC joint injections within the last 3 months or scheduled in the next 3 months.
- Any GC intake expected more than $>5\text{mg/day}$ within the next 12 months (i.e. administration with rituximab, multiple sclerosis requiring frequent GC infusions,...).
- Any disease with GC contraindication.
- Association with sultopride and with live vaccines.
- Significant trauma or major surgery within the 3 months prior to the baseline visit.
- Scheduled surgery in the next 12 months.
- Fibromyalgia.
- Foreseeable poor compliance with the strategy.

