- Hypotension.
- Biological abnormality such as hyponatremia, hyperkalemia, renal salt loss and hypoglycemia.

If an acute adrenal insufficiency is suspected, an extra visit will be performed in emergency and if the acute adrenal insufficiency is confirmed, the patient will be hospitalized to be treated at the choice of the investigator. If the serum cortisol dosage confirms clinical adrenal insufficiency, an open hydrocortisone therapy by hydrocortisone 20mg/d will be started and an appointment with the endocrinologist will be made. If the serum dosage does not confirm adrenal insufficiency, hydrocortisone will be stopped and other causes of the symptoms will be investigated. If no severe concomitant disease is found, the patient will be able to go back to her/his step of the protocol.

All clinical adrenal insufficiency reports will be reviewed by an independent committee to decide whether, according to the report, the diagnosis of clinical adrenal insufficiency can be validated and recorded for the study. This will be declared as a serious adverse event.

It is expected that less than 1% of patients in this study will experience clinical adrenal insufficiency.

3. Proportion of patients with biological adrenal insufficiency.

Two blood tests will be scheduled with a Synacthène® test at 4 and 7 months. A pathological Synacthène® test will be diagnosed if one hour after Synacthène®, serum cortisol is below 200 ng/mL or 600 nmol/L, or 20 µg/100 ml. In case of abnormal test at the latest Synacthène® test another Synacthène® test will be realized at M12.

4. Proportion of patients who needed a short rescue GC treatment during the protocol.
5. Proportion of patients who needed a GC intra-articular or peri-articular injection during the protocol related to the RA.
6. Proportion of patients with a flare confirmed by the clinician. In case of symptoms of flare, the patient will have an extra visit at her/his center. For DAS28 >3.2, a flare will be confirmed. A flare will be also diagnosed if the DAS28 is >3.2 at any scheduled visits.
7. The area under the curves of the self-administered Flare Assessment in Rheumatoid Arthritis (FLARE) questionnaire. FLARE is an approved self-assessment questionnaire that will be completed at each visit and in case of FLARE at home by the patient. The results are expressed as continuous data. The area under the curve of all the questionnaires will be the variable analyzed.

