 - Treatment of a flare-up by the attending physician (yes/no) [CRF p44]
 - Other, specify (yes/no) [CRF p44]
- 3/ Corticosteroid infiltration has it been carried out since the last consultation? (yes /no) [CRF p44]
 - If Yes, specify:
 - The reason :
 - Related to RA (yes/no) [CRF p44]
 - The number of infiltrations received [CRF p44]
 - Not related to RA (yes/no) [CRF p44]
 - The number of infiltrations received [CRF p44]
 - Precision
- 4/ Has hydrocortisone treatment been received in addition to the protocol since the last consultation? (yes /no) [CRF p44]
 - If Yes, specify:
 - The dose received (mg/day) [CRF p44]
 - The reason :

STAR – Statistical Analysis Plan
V3, June 2023

Page 40 of 96

- Acute adrenal insufficiency (yes/no) [CRF p44]
 - Clinical signs of chronic adrenal insufficiency (yes/no) [CRF p44]
 - Biological signs of chronic adrenal insufficiency (yes/no) [CRF p44]
 - Prescribed in the context of traumatic stress, infectious during surgery (yes/no) [CRF p44]
 - Other, precision [CRF p44]
- Has the patient had a flare-up of his illness documented by a doctor (defined by a DAS28 \geq 3.2) since the last visit? (yes /no) [CRF p34]

Basic treatment at M4

- Change in background treatment since the last visit (yes/no) [CRF p 45]
- If yes, complete:
 - Background treatment was reduced (yes/no) [CRF p 45]
 - If yes, reason (Remission or low level of activity/Tolerance problem/Other) [CRF p45]
 - Background treatment was stopped
 - If yes, reason (Remission or low level of activity/Tolerance problem/Ineffectiveness/Other) [CRF p45]
 - The basic treatment has been increased
 - If yes, reason (Ineffectiveness/Other) [CRF p45]
 - The background treatment has been replaced
 - If yes, reason (I neffectiveness/Intolerance/Other) [CRF p45]

NSAID treatments at M4

- Current oral NSAID intake (even occasional) (yes/no) [CRF p 46]

STAR – Statistical Analysis Plan
V3, June 2023

Page 41 of 96

Bone densitometry at inclusion (ITT population)

- Osteodensitometry performed (yes/no) [CRF p15]
- If yes, complete:
 - Spine T score [CRF p15]
 - T score pass [CRF p15]
- Vitamin-calcium supplementation (yes/no) [CRF p15]
- If yes, complete:
 - Type of supplementation (Vitamin D/Calcium/Both) [CRF p15]

STAR – Statistical Analysis Plan
V3, June 2023

Page 42 of 96

Biological assessment at inclusion (ITT population)

- Biological assessment carried out (yes/no) [CRF p17]
- VS in the first hour (mm) [CRF p17]
- CRP (mg/L) [CRF p 17]

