 - Withdrawal of consent (yes/no) [CRF p157]
 - Death (yes/no) [CRF p157]
 - Patient lost to follow-up (yes/no) [CRF p157]
 - Protocol violation (yes/no) [CRF p157]
 - Specify (listing) [CRF p157]
 - Other (yes/no) [CRF p157]
 - Specify (listing) [CRF p157]
- Has the blind been lifted? (yes /no) [CRF p157]
 - The reason for unblinding (listing) [CRF p157]

STAR – Statistical Analysis Plan
V3, June 2023

Page 56 of 96

ANALYSIS OF THE MAIN JUDGMENT ENDPOINT

1) Redefinition of the primary endpoint (ITT)

The primary endpoint is the proportion of patients who were able to wean off prednisone or hydrocortisone (success rate) in each group at the end of the study (12 months).

The withdrawal strategy will be considered a failure for:

- Patients who are still receiving oral prednisone and/or hydrocortisone at the end of the study. [Modality 1](#)
- Patients who received more than two intra-articular or periarticular injections during the entire study to treat RA-related synovitis, bursitis, or tenosynovitis. [Modality 2](#)
- Patients who received more than two short GC therapies during the entire study period. [Modality 3](#)
- Patients who presented clinical or biological signs of adrenal insufficiency leading to the use of hydrocortisone until the end of the protocol. [Modality 4](#)
- Patients who received more than two weeks of GC for a reason other than their illness. [Modality 5](#)

Variable name	Derivations

Total number of infiltrations received in relation to RA over the duration of post-randomization follow-up
	
From the variable “ number of infiltrations received ” [CRFp44, p69, p94, p111], we will create a discrete quantitative variable from the number of infiltrations carried out between each visit.
 
The value of this variable will correspond to the sum of all infiltrations carried out if:
 
 • “ was a corticosteroid infiltration carried out ” = yes • AND “ related to RA ” = yes 
 ○ AND “ the number of infiltrations received ” = not missing 
It will take the value 0 in all other cases.

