
Prednisone/hydrocortisone at the end of the study (yes/no)
 
Modality 1
	
From the variables of [CRFp110 and p111] to M12, we define 2 modalities:
 
 • “If yes”: 
 ○ “Has the patient received corticosteroid treatment with prednisone, prednisolone or methylprednisolone since the last visit?” = yes 
 AND 
 ▪ “Has treatment with oral corticosteroids been received in addition to the treatment prescribed as part of the protocol since the last visit?” = yes ▪ OR if “Has hydrocortisone treatment been received in addition to the protocol since the last consultation?” = yes • “No” in all other cases

STAR – Statistical Analysis Plan
V3, June 2023

Page 59 of 96

Variable name	Derivations

More than 2 joint injections during the study period (yes/no)
 
Modality 2
	
From the variable “ Total number of infiltrations received in relation to RA ” [Derived variable], we define 2 modalities:
 
 • " If yes : 
 ○ “ Total number of infiltrations received in relation to RA ” [Derived variable] > 2 • " Not if : 
 ○ “ Total number of infiltrations received in relation to RA ” [Derived variable] ≤ 2

More than 2 short GC therapies corresponding to rescue treatment for the entire duration of the study (yes/no)
 
Modality 3.1
	
From the variable “ Total number of assaults ” [Derived variable], we define 2 modalities:
 
 • " If yes : 
 ○ “ Total number of attacks corresponding to emergency treatment ” [Derived variable] > 2 • " Not if : 
 ○ “ Total number of attacks corresponding to rescue treatment ” [Derived variable] ≤ 2

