
Taking at least one short GC therapy not corresponding to rescue treatment for the entire duration of the study (yes/no)
 
Condition 3.2
	
From the variable “ Total number of assaults ” [Derived variable], we define 2 modalities:
 
 • " If yes : 
 ○ “ Total number of attacks not corresponding to rescue treatment ” [Derived variable] ≥ 1 • " Not if : 
 ○ “ Total number of attacks not corresponding to emergency treatment ” [Derived variable] = 0

Clinical or biological signs of adrenal insufficiency treated with hydrocortisone at the end of the protocol (yes/no)
 
Modality 4
	
From the variables of [CRFp111] to M12, we define 2 modalities:
 
 • " If yes : 
 ○ “ Has hydrocortisone treatment been received in addition to the protocol since the last consultation? » = yes 
 ▪ AND “ Hydrocortisone end date ” = in progress ▪ AND Reason: “ Acute adrenal insufficiency ” = yes 
 • OR “ Clinical signs of chronic adrenal insufficiency ” = yes • OR “ Biological signs of chronic adrenal insufficiency ” = yes • “No” otherwise

Variable name	Derivations

More than 2 weeks of GC for reasons other than their illness (yes/no)
 
Modality 5
	
From the variable “ Number of days of taking GC for reasons other than their illness (in days) ” [Derived variable], we define 2 modalities:
 
 • “ If yes : 
 ○ “ Number of days of taking GC for other reasons ” [Derived variable] > 15 • “ Not if : 
 ○ “ Number of days of taking GC for other reasons ” [Derived variable] ≤ 15

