If acute adrenal insufficiency is suspected, an additional visit will be performed as an emergency and if acute adrenal insufficiency is confirmed, the patient will be hospitalized for treatment at the discretion of the investigator. If the serum cortisol dosage confirms clinical adrenal insufficiency, open therapy with hydrocortisone 20 mg/day will be started and an appointment with the endocrinologist will be made. If the serum level does not confirm adrenal insufficiency, hydrocortisone will be stopped and other causes of the symptoms will be sought. If no serious concomitant illness is found, the patient can resume treatment. All reports of clinical adrenal insufficiency will be reviewed by an independent committee to decide whether, according to the report, the diagnosis of clinical adrenal insufficiency can be validated and recorded for the study. This deficiency will be reported as a serious adverse event.

It is anticipated that less than 1% of patients in this study will have clinical adrenal insufficiency.

The proportion of patients with acute adrenal insufficiency will be described in both groups. This result will be expressed as a percentage. We anticipate that less than 1% of patients included in this study will experience acute adrenal insufficiency and therefore no tests are planned for comparison.

For this analysis, the variable **“Acute adrenal insufficiency”** [CRF p111] will be described in the two groups.

STAR – Statistical Analysis Plan
V3, June 2023

Page 67 of 96

3) Proportion of patients with biological adrenal insufficiency at one year

Proportion of patients with biological adrenal insufficiency.

Two blood tests will be scheduled with a Synacthène® test at 4 and 7 months. A pathological Synacthène® test will be diagnosed if, one hour after Synacthène®, serum cortisol is below 200 ng/mL or 600 nmol/L, or 20 µg/100 ml. In the event of an abnormal test, at the latest, another Synacthène® test will be carried out at M12.

Variable name	Derivations

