
Presence of biological adrenal insufficiency at one year (yes/no)
	
From the variables “ Test performed (Synacthen test) (yes/no) ” at M12 [CRFp127], “ Is the Synacthen test considered pathological? (yes /no) ” to M12 [Derived variable], “ Has hydrocortisone treatment been received in addition to the protocol since the last consultation? » and “ Biological signs of chronic adrenal insufficiency ” [CRFp111], we define 2 modalities:
 
" If yes :
 
 • “ Test carried out (Synacthen test) ” = Yes • AND “ Is the Synacthen test considered pathological? » = Yes 
OR
 
 • “ Has hydrocortisone treatment been received in addition to the protocol since the last consultation? » = Yes • AND “ Biological signs of chronic adrenal insufficiency ” = Yes 
" Not if :
 
 • “ Test carried out (Synacthen test) ” = No • AND “ Has hydrocortisone treatment been received in addition to the protocol since the last consultation? » = No 
OR
 
 • OR if “ Test carried out (Synacthen test) ” = Yes • AND “ Is the Synacthen test considered pathological? » = No • AND “ Has hydrocortisone treatment been received in addition to the protocol since the last consultation? » = No

STAR – Statistical Analysis Plan
V3, June 2023

Page 68 of 96

4) Proportion of Patients Needing Supplemental Prednisone to Control Flares

Proportion of patients who required salvage GC treatment during the protocol.

To meet this secondary endpoint, we will use the Treatment Compliance Variables at M4, M7, M9, M12, Vadd 1 and Vadd2 which will be combined to create a new binary derived variable as presented below :

Variable name	Derivation

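### Secondary endpoint 2 (acute adrenal insufficiency) is read from the M12 page only, so it misses episodes whose hydrocortisone ended before the previous consultation and episodes in patients with no M12 page

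*SAP*

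**What the plan says.** Section 2 of the SAP's analyses of secondary criteria gives a clinical description of acute adrenal insufficiency. It plans no test because fewer than 1% of patients are expected to have it. It then names one source: "CRF p111] will be described in the two groups".

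Two other places show what that page is. The derivation of Modality 1 of the primary endpoint places it at the final visit: "From the variables of [CRFp110 and p111] to M12, we define 2 modalities". The derivation of Modality 4 shows that acute adrenal insufficiency on p111 is one of the reasons listed under the question "Has hydrocortisone treatment been received in addition to the protocol since the last consultation".

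The same item is on the M4 page, in the list headed Compliance with treatment at M4: "Acute adrenal insufficiency (yes/no) [CRF p44".

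The definition of the endpoint, in the Endpoints section, adds a validation step: "All clinical adrenal insufficiency reports will be reviewed by an independent committee". Cases are also to be declared as serious adverse events, which have an objective of their own: "To compare the proportion of patients with “serious” adverse events at 1 year between the groups".

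**The concern.** An acute episode can occur at any time while steroids are being reduced. The plan looks for it on a page completed at M12 that asks only about the interval since the previous consultation. The treatment phase is over before that interval opens.

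The field is also not the endpoint as defined. The SAP wants cases reviewed and validated by an independent committee, but the p111 item records only a reason for giving hydrocortisone.

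At stake is the count that will be published for a risk which the SAP's rationale names among the hazards of steroid withdrawal. If the derivation is programmed as written, the line for this endpoint may show fewer cases than the serious adverse event listing in the same report, with nothing to explain the difference.

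**Working it through.** **Pages and visits.** The derivation for joint injections lists parallel pages for the four scheduled visits: "CRFp44, p69, p94, p111], we will create a discrete quantitative variable". These correspond to M4, M7, M9 and M12. Page 111 is therefore the M12 page and the consultation before it is nominally M9. The window is shorter if an additional visit came in between.

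**Treatment phase.** Randomisation is at M1. The sample size section gives two hydrocortisone steps of 3 months each, so study treatment runs from M1 to 1 + 3 + 3 = M7.

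**Share of follow-up covered.**
- Window on p111: (12 − 9)/(12 − 1) = 3/11 = 27%.
- Outside the window: (9 − 1)/11 = 8/11 = 73%, which includes all of M1–M7 (6/11 = 55%).

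**Effect on the count.** The SAP gives no sample size or power for this endpoint. Its only figure is a rate below 1%. Take N = 102 randomised patients and three rates p at or under that ceiling. Assume that events are spread evenly over M1–M12, that hydrocortisone for earlier episodes ended before M9, and that nobody is lost. Then:
- expected events, whole period: 102p
- expected events, p111 window: 102p × 3/11
- chance of at least one event, whole period: 1 − (1 − p)^102
- chance of at least one event, p111 window: 1 − (1 − 3p/11)^102

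| p | Expected, M1–M12 | Expected, window | Chance of ≥1, M1–M12 | Chance of ≥1, window |
|---|---|---|---|---|
| 1% | 1.02 | 0.28 | 64% | 24% |
| 0.5% | 0.51 | 0.14 | 40% | 13% |
| 0.2% | 0.20 | 0.06 | 18% | 5% |

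At the ceiling, 1.02 − 0.28 = 0.74 expected events fall outside the window.

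**Patients without an M12 page.** The sample size section allows for 20% loss to follow-up, about 0.20 × 102 = 20 patients. The end-of-study sheet lists an adverse event as one reason for stopping early. The section on handling missing data gives a rule for the primary endpoint and for explanatory variables, but none for this endpoint.

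**Committee decision.** If serum cortisol does not confirm the diagnosis, the SAP has hydrocortisone stopped. A suspected case that was later refuted could therefore still be ticked as a reason. The field can err both ways: it can miss validated cases and include unvalidated ones.

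**How the SAP treats similar endpoints.** Joint injections are summed over p44, p69, p94 and p111. For rescue steroids, "we will use the Treatment Compliance Variables at M4, M7, M9, M12, Vadd 1 and Vadd2". Endpoint 2 is tied to one page although the SAP already pools visits elsewhere.

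**The case against.** There are five points on the other side.

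1. **A reader might infer that the trial's main safety outcome loses every early event.** The SAP supports neither half of that. It ranks this as the second secondary endpoint, described without a test. An early episode whose hydrocortisone continued past M9 can still be ticked on p111. Modality 4 relies on this, since it combines the acute reason with hydrocortisone still in progress at M12. This objection stands and narrows the point to the two groups named in the heading.

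2. **Early episodes are reported elsewhere.** They are to be declared as serious adverse events. These are counted per patient over the year in secondary endpoint 13, and in the safety section they are listed by preferred term with dates and presented by arm. This stands too: the event is not lost to the trial report. However, endpoint 13 counts any serious event, so it does not replace a count of this one.

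3. **The wording at one year could mean status at M12.** Endpoint 3 carries the same wording and is also built on M12 variables. But the analysis text for endpoint 2 speaks of patients who will experience the event and has every report reviewed. That describes a proportion accumulated over the study, so the objection does not rescue the derivation.

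4. **The page reference may simply be incomplete.** Other references in the SAP look unreliable: p27 is cited for the EQ-5D at M12, and the M4 flare item is given as p34 in one place and p45 in another. That may be the cause here, but a programmer will follow the text as written, and the correction is the same.

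5. **Part of the remedy rests on inference.** The acute item is shown only for p44 and p111. Its presence on p69 and p94 is inferred from the repeated layout. For the additional visits, the SAP shows suggestive clinical signs as a reason for the visit, not a validated diagnosis. This stands, and it is why the fix starts from the committee decisions and the adverse event pages.

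**Conclusion.** The point holds in its narrow form. As written, secondary endpoint 2 has a nominal window of 3 of 11 post-randomisation months that opens after the whole treatment phase. It misses episodes whose hydrocortisone ended before the previous consultation and episodes in patients with no M12 page. It also carries no committee decision.

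The fall from 1.02 to 0.28 expected events at the 1% ceiling rests on even timing, no losses, and hydrocortisone for earlier episodes finished by M9. The SAP states none of these. Where hydrocortisone continued past M9, the shortfall is smaller. The 27% is a share of time and becomes a share of events only under those assumptions.

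The consequence is a possible undercount in one descriptive line and a possible disagreement with the serious adverse event table. The primary analysis is unaffected, and the safety section should still show the events. It merits correction before the database is frozen, but it does not threaten the trial's conclusions.

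**What to change.** Amend the analysis section for secondary endpoint 2 as follows.

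- **Definition:** the proportion of patients with at least one acute adrenal insufficiency validated by the independent committee, from first study dose to M12.
- **Case finding:** the committee's decisions and the adverse event pages (p169–171).
- **Cross-check:** the hydrocortisone-reason item on p44 and p111, the parallel pages p69 and p94 once the item is confirmed to be there, and the additional-visit pages. Explain any discrepancy in a listing.
- **Patients who leave early:** count any validated episode up to their last contact, and state how many patients have no M12 page.
- **Reporting:** counts and percentages by arm, still without a test, reconciled with the serious adverse event listing.

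The cost is a signed SAP amendment and some programming. The sources are pages the SAP already cites and committee decisions it already requires. The one thing to verify is that the item appears on p69 and p94. No new data collection is needed for the main definition.

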According to the 2013 update of the European League Against Rheumatism (EULAR) recommendations for the management of rheumatoid arthritis (RA), glucocorticoid (GC) withdrawal should be considered in patients reaching a target of remission or low disease activity to prevent or minimize the adverse effects of long-term GC therapy. While GCs are widely used in RA and GC withdrawal exposes RA patients to flare, joint destruction, withdrawal syndrome and adrenal insufficiency, there is an unmet need for an effective and safe GC withdrawal strategy to decrease these risks and increase the rate of effective GC withdrawal. Hydrocortisone replacement therapy has been proposed as a potential strategy to decrease the risk of GC withdrawal syndrome and adrenal insufficiency in patients subject to long-term GC therapy. We hypothesise that this strategy, which has never been investigated in RA, may increase the probability of GC withdrawal and decrease the risk of adverse events in RA patients who are candidates for GC withdrawal.

2) Study Design

This study is a national multicenter double-blind parallel arm, phase IV, controlled 1:1 randomized trial of superiority comparing two strategies of GC withdrawal in patients in remission or low disease activity:

- **Group 1:** tapering prednisone using a pre-defined schedule and hydrocortisone placebo (GC tapering group).
- **Group 2:** replacing prednisone with hydrocortisone and a prednisone placebo with a predefined schedule for tapering the prednisone placebo (hydrocortisone replacement group).

Randomization will be performed if DAS28 is lower than 3.2 after one month of a stable dose of prednisone 5 mg/day, and will be stratified on the center and the length of the GC duration before the beginning of the study.

STAR – Statistical Analysis Plan
V3, June 2023

Page 8 of 96

3) Primary Objective

To compare a prednisone tapering strategy to a hydrocortisone replacement strategy on the success rate of prednisone and hydrocortisone withdrawal at one year in RA patients in low disease activity or remission.

4) Secondary Objectives

1. To compare the proportion of patients who could withdraw from prednisone whatever the additional hydrocortisone associated treatment.
2. To compare the proportion of patients with acute adrenal insufficiency at one year between the two groups.
3. To compare the proportion of patients with biological adrenal insufficiency at one year between the two groups.

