- Tobacco consumption (no/yes, patient weaned/yes, current) [Derived variable]
- Corticosteroid therapy before inclusion (≤ 2 years / > 2 years) [CRF p 19]

Visits made and reasons

- M4 visit carried out (yes/no) [CRF p43]
 - If no, specify the reason (listing) [CRF p43]
- M7 visit carried out (yes/no) [CRF p68]
 - If no, specify the reason (listing) [CRF p68]
- M9 visit carried out (yes/no) [CRF p93]
 - If no, specify the reason (listing) [CRF p93]
- M12 visit carried out (yes/no) [CRF p110]
 - If no, specify the reason (listing) [CRF p110]
- VA1 visit carried out (yes/no) [Derived variable]
 - Reason for additional visit: [CRF p135]
 - Disease outbreak according to patient (yes/no) [CRF p135]
 - Disease outbreak according to doctor (yes/no) [CRF p135]
 - Adverse events (yes/no) [CRF p135]
 - Clinical signs suggestive of adrenal insufficiency [CRF p135]
 - Other (yes/no) [CRF p135]
- VA12 visit carried out (yes/no) [Derived variable]
 - Reason for additional visit: [CRF p146]
 - Disease outbreak according to patient (yes/no) [CRF p146]
 - Disease outbreak according to doctor (yes/no) [CRF p146]
 - Adverse events (yes/no) [CRF p146]
 - Clinical signs suggestive of adrenal insufficiency [CRF p146]
 - Other (yes/no) [CRF p146]

Characteristic of the disease on the day of the inclusion visit, at M1, at M4

Doctor questionnaire at inclusion, M1

- Weight (kg) [CRF p15 , p23, p47]
- Size (cm) [CRF p15]
- Systolic blood pressure (mmHg) [CRF p15 , p23, p47]
- Diastolic blood pressure (mmHg) [CRF p15 , p23, p47]
- High blood pressure (yes/no) [Derived variable]

Elements of DAS28 at inclusion, M1

- DAS28 score [CRF p15 , p23, p47]
- Number of painful joints [CRF p15 , p23, p47]
- Number of swollen joints [CRF p15 , p23, p47]

STAR – Statistical Analysis Plan

V3, June 2023

Page 31 of 96

- Overall assessment of the activity by the doctor (/ 10)

[CRF p15 , p23, p47]

Patient questionnaire at inclusion, at M1, at M4

- Presence of nocturnal awakenings linked to pain (yes/no)
- Duration of joint stiffness in the morning (minutes)
- Pain (0 to 10)
- Overall assessment of disease activity (0 to 10)
- Fatigue (from 0 to 10)

[CRF p16 , p23, p48]

[CRF p16 , p23, p48]

[CRF p16 , p23, p48]

[CRF p16 , p23, p48]

[CRF p16 , p23, p48]

STAR – Statistical Analysis Plan
V3, June 2023

Page 32 of 96

Comorbidities associated with RA (ITT population)

- History of clinical myocardial infarction (yes/no) [CRF p14]

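### Acute adrenal insufficiency at one year is derived from a single M12 item, so an episode whose extra hydrocortisone ended before the last consultation is missed by this endpoint

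*SAP*

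**What the plan says.** Secondary objective 2 is "To compare the proportion of patients with acute adrenal insufficiency at one year between the two groups". Under Endpoints (secondary endpoint 2), the SAP sets a path for each case: "If an acute adrenal insufficiency is suspected, an extra visit will be performed in emergency". An independent committee then decides whether the diagnosis is validated and recorded, and the case is declared a serious adverse event.

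The analysis section for this endpoint (Analyzes of secondary judgment criteria, 2) repeats that path. It plans a percentage per group without a test, because fewer than 1% of patients are expected to have the event. It has no derivation table. The only data source named is the acute adrenal insufficiency variable, "CRF p111] will be described in the two groups".

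Modality 4 in the redefinition of the primary endpoint shows where that variable sits. It is one of the reasons listed under the question "Has hydrocortisone treatment been received in addition to the protocol since the last consultation".

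**The concern.** The objective, the emergency visit and the committee review all describe episodes that may occur at any time in follow-up. The derivation reads one late item with a short look-back, although the same item is printed for M4 and other endpoints pool several visits.

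Adrenal insufficiency is one of the risks of withdrawal named in the SAP's rationale, and reducing it is part of the case for hydrocortisone replacement. No test is planned, so the described percentage is the entire result for this objective. If the plan is followed as written, the endpoint could show 0% in both arms while the serious adverse event listing contains a validated episode.

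**Working it through.** **1. Which visit page 111 belongs to.** Modality 1 of the primary endpoint reads: "From the variables of [CRFp110 and p111] to M12, we define 2 modalities". Pages 110 and 111 are therefore M12 pages.

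**2. What the item looks back on.** Its parent question concerns hydrocortisone received since the last consultation. The visit list has "M9 visit carried out (yes/no) [CRF p93", so M9 is the last scheduled visit before M12. The window applies to hydrocortisone use, not to onset of the episode.

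**3. Length of the window, on the scheduled calendar.** Randomisation is at M1 and the study ends at M12 (Sample size calculation; Endpoints).
- Follow-up after randomisation: 12 − 1 = 11 months.
- Read by the M12 item: 12 − 9 = 3 months; 3/11 = 27%.
- Not read: 8/11 = 73%.
- Hydrocortisone in group 2 runs 3 + 3 months from M1, so it ends at M1 + 6 = M7, two months before the window opens.

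**4. Which episodes the item can and cannot show.**

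| Episode | Item on p111 |
|---|---|
| Open hydrocortisone received at some time after the last consultation, whatever the onset date | Can be ticked |
| Open hydrocortisone ended before the last consultation | Missed |
| Patient has no M12 page | Missed; no rule is given for this endpoint |

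On the last row, the SAP anticipates 20% loss to follow-up: 0.20 × 102 = about 20 randomised patients. Its rule that losses count as failures applies to the primary endpoint.

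**5. What the SAP reads elsewhere.** The M4 compliance section prints "Acute adrenal insufficiency (yes/no) [CRF p44", the same item. For infiltrations the SAP pools four visit pages: "CRFp44, p69, p94, p111], we will create a discrete quantitative variable". The intravenous or intramuscular corticosteroid variable uses the same four pages and adds the two additional visits; the flare endpoint also includes those visits. Endpoint 2 pools nothing. The SAP prints the acute adrenal insufficiency item only for p44 and p111. Its presence on p69 (M7) and p94 (M9) is an inference from parallel page layout.

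**6. Cumulative or status at M12.** Secondary objective 13 is also worded as at 1 year, yet its endpoint is at least one serious adverse event over one year, so the SAP uses that phrase for cumulative occurrence. Its expected rate for acute adrenal insufficiency refers to patients who will experience the event. Where the SAP wants status at the end of study, as in Modality 4, it also requires hydrocortisone to be still in progress. Endpoint 2 has no such condition, so the item as read measures neither quantity.

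**7. Scale, as an illustration.** The SAP gives only an expected rate below 1%; 2% and 5% are assumed here to show a range. Assume also a constant rate from M1 to M12 and, as the worst case for the item, no earlier episode with hydrocortisone continuing past M9. Expected episodes = 102 × p; expected in the window = 102 × p × 3/11.

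| p | Episodes expected | In the M9 to M12 window |
|---|---|---|
| 1% | 1.02 | 0.28 |
| 2% | 2.04 | 0.56 |
| 5% | 5.10 | 1.39 |

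At 1%, the chance of at least one episode in the trial is 1 − 0.99^102 = 0.64. The chance of at least one in the window is 1 − (1 − 0.01 × 3/11)^102 = 0.24.

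**The case against.** **Earlier cases may still be counted.** A confirmed case starts open hydrocortisone, and a patient still taking it after M9 can be ticked at M12. A reader might infer that every episode before M9, or every episode handled at the extra visit, is lost. The documents do not support that. Even if an extra visit counts as the last consultation, which the SAP does not say, hydrocortisone started there may be received afterwards and so be reported at M12. This limits the point to the cases marked as missed in the table.

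**The episode is not lost to the trial.** A reader might infer that an arm difference during tapering could not appear anywhere. That is also unsupported. Each case is declared a serious adverse event. The safety section lists events with preferred term and start date and presents adverse event incidence by arm, and endpoint 13 covers patients with any serious adverse event. The M4 item and the extra-visit reason of suggestive clinical signs are in the planned descriptive tables. This objection stands, and it lowers the severity. It does not correct the endpoint's own percentage.

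**At one year may mean status at M12.** Endpoint 3 (biological adrenal insufficiency), also worded this way, is built on M12 fields. The wording is open, but the item fails as a status measure too, for want of an in-progress condition.

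**Counting every tick would over-count.** This also stands. The SAP requires committee validation before the diagnosis is recorded, so pooling all ticks would replace one error with another.

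**Conclusion.** The point holds in a limited form. Endpoint 2, read as cumulative occurrence, is derived from an item that normally covers hydrocortisone use in 3 of the 11 months after randomisation. It misses episodes whose open hydrocortisone ended before the last consultation and episodes in patients with no M12 page. Its percentage can therefore disagree with the serious adverse event listing.

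The 73% is an upper bound on the gap in the window for a patient seen at M9 and M12. It should not be read as the share of episodes lost: that depends on when episodes occur and how long hydrocortisone continues, and the SAP gives neither. With about one episode expected at most, the practical effect is either none or the whole result.

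The conclusion assumes that p111 has the same layout as the M4 page, which Modality 4 supports, and that the endpoint is meant to be cumulative. It does not touch the primary analysis. The endpoint is secondary, descriptive and untested, so this is a should-fix.

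**What to change.** In the analysis section for endpoint 2:

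- State that the endpoint is the proportion of patients with at least one acute adrenal insufficiency from randomisation to end of study.
- Derive yes from any episode validated by the independent committee, not from a tick alone.
- Identify candidate episodes from the serious adverse event tables (CRF p169-171), the item at M4 (p44) and M12 (p111), the M7 and M9 pages (p69, p94) if they carry the item, and the additional-visit forms.
- Reconcile these sources with each other and with the committee's decisions before the database is frozen.
- Say how patients without an M12 page are handled.
- Describe the proportion by arm, with date of onset.

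The cost is one rewritten derivation and one reconciliation step. The committee review and serious adverse event reporting are already planned, so no new data collection should be needed. Whether p69, p94 and the additional-visit forms record the diagnosis itself has to be checked against the CRF.
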